3.2.3 Participant Restrictions During the Study

3.2.3.1 General and Dietary

To avoid false positive results for drugs of abuse tested at the Screening Visit, participants should refrain from food or drink containing poppy seeds (e.g., specialty breads and muffins) for 72 hours before the Screening Visit.

3.2.3.2 Contraception and Pregnancy Avoidance Procedures

Female participants who are not of childbearing potential (defined as any female who has experienced menarche and who is NOT permanently sterile or postmenopausal) must be postmenopausal, as defined in Glossary of Terms, or surgically sterile (e.g., hysterectomy, bilateral tubal ligation, or bilateral oophorectomy). NOTE: These procedures and/or laboratory test results must be confirmed by physical examination or be provided through medical documentation. If of childbearing potential, female participants must be practicing a medically approved and highly effective method of contraception (Glossary of Terms).

All female participants of childbearing potential must have a negative urine pregnancy test result at the Screening Visit and before vaccine administration. Women of childbearing potential must agree to be heterosexually inactive or to consistently use acceptable methods of contraception, as defined in Glossary of Terms, from at least 30 days before the first vaccination through 3 months after the last vaccination.

Male participants must agree to practice adequate contraception (Glossary of Terms) from the time of first vaccination through 3 months after the last vaccination. Males must also agree to refrain from donation of sperm from the time of first vaccination through 3 months after the last vaccination.

Periodic abstinence, declaration of abstinence for the duration of the study, and withdrawal are not acceptable methods of contraception for male or female participants.

Female participants of childbearing potential and male participants will be provided with information on acceptable methods of contraception as part of the participant informed consent process and will be asked to sign a consent form stating that they understand the requirements for avoidance of pregnancy.

3.3 Withdrawal of Participants From the Study or Study Dosing

3.3.1 Participant Withdrawal From the Study

Participants can withdraw consent and discontinue from the study at any time, for any reason, without prejudice to further treatment the participant may need to receive.

If participant desires to withdraw from the study because of an AE, the investigator will try to obtain agreement to follow up with the participant until the event is considered resolved or stable and will then complete the EOS electronic case report form (eCRF).

Potential reasons for withdrawing a participant from the study include the following:

- SAE
- AE (non-SAE)
- Protocol violation (specify)
- Consent withdrawal (document the reason)
- Lost to follow-up
- Other (specify)

Participants who are withdrawn from the study will be requested to complete the EOS (Visit 20 [Month 13]) assessments. The reason for participant withdrawal or lost to follow-up will be documented, as detailed in Section 3.3.3.

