3.3.3 Handling of Withdrawals

When a participant withdraws from the study, the reason(s) for withdrawal will be recorded by the investigator on the relevant page of the eCRF. These participants will also be requested to complete the EOS (Visit 20 [Month 13]) assessments.

Any participant who fails to return for final assessments will be contacted by the site with a minimum of 3 documented telephone calls, faxes, text messages, or emails and 1 registered mail letter. If participant is not reached, the participant will be defined as lost to follow-up. All attempts to contact the participant must be documented in the participant's source

documents. After the final attempt, the participant will be declared "lost to follow-up" at the EOS Visit.

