6	Any ≥ Grade 3 unsolicited adverse event in an mRNA-1893 cohort ^b that cannot be reasonably attributed to a cause other than vaccination OR Any ≥ Grade 3 laboratory abnormality ^c in an mRNA-1893 cohort ^b that cannot reasonably be attributed to a cause other than vaccination	≥ 20% and ≥ 2 participants/group	

^a For the first 5 participants in each dose level cohort, the pause rule will be considered met if 2 of the first 5 participants experience the same event regardless of dosing group.

If a pause is triggered in the study, each participant's clinic visits will continue until the next scheduled vaccination visit. If a pause affects a participant's vaccination visit, the window for that participant's vaccination visit will be suspended until the pause is lifted and vaccination can resume. Once the pause is lifted at a site, vaccination should be reinstated as soon as possible. Clinic visits should thereafter (Day 36 [+3 days], Day 57 [-7/+14 days], Month 7 [± 14 days], and Month 13 [± 14 days]) be scheduled as if participants had received their second vaccination within the 28 (+14) day window. The Dose 2 window may be extended to 28 (+14) days at the discretion of the principal investigator and with approval of the study medical monitor on a case by case basis for participants whose window is affected by a study pause.

b The rate of adverse events and laboratory abnormalities will be computed based on the number of exposed participants who have provided safety data (i.e., have completed a post-dosing visit for assessment of safety).

Grading of laboratory parameters will be based on the US Food and Drug Administration Guidance for Industry "Toxicity grading scale for healthy adult and adolescent volunteers enrolled in preventive vaccine clinical trials" (DHHS 2007).

If a pause is prolonged such that the second vaccination takes place outside the 28 (+14) day window, the Sponsor has the option to add additional participants in a dosing cohort to achieve the original number of participants planned for dosing within the 28 (+14) day window. If a participant is in the Screening Phase for more than 28 days as the result of a pause, the participant may be rescreened for study eligibility (and will receive a new screening number) as long as the participant continues to provide consent to participate in the study.

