3.6 Statistical Analysis Plans

3.6.1 Primary Endpoints

The following are the primary endpoints of the study:

• Frequency and grade of each solicited local and systemic reactogenicity AE during a 7-day follow-up period after each vaccination

- Frequency and grade of any unsolicited AEs during the 28-day follow-up period after each vaccination
- Frequency of any MAAE, SAE, and AESI from Day 1 to the EOS Visit at Month 13

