6 APPENDICES

6.1 Appendix 1: Schedule of Events

The Schedule of Events is presented in Table 5.

Table 5: Schedule of Events

Procedure	Screening Phase				Vaccina	tion Phas	e				Loi	ng-Teri	m Follow-	up Phase
Study Visit	Screening	Day 1	Day 2	Day 3	Day 8	Day 29	Day 30	Day 31	Day 36	Day 57 (Month 2)	Months 3, 4, 5, 6		Months 8, 9, 10, 11, 12	Month 13 (EOS) ^a
Visit Number	0	1	2	3	4	5	6	7	8	9	10-	14	15-19	20
Type of Visit	C	C	SC	SC	C	C	SC	SC	C	C	SC	C	SC	C
Window Allowance	-28/0	0	0	0	+3	+14	0	0	+3	-7/+14	±7	±14	±7	±14
Informed consent	X	_	_	_	_	_	-	_	_	_	_	_	_	_
Inclusion/exclusion criteria	X	X	-	_	-	1	_	_	_	ı	_	_	_	-
Baseline demographics	X	_	_	_	_	_	_	_	_	_	_	_	_	_
Medical and prior medication history	X	_	_	_	_	_	_	_	-	_	_	-	_	_
Concomitant medications, including vaccinations	X	X	X	X	X	X	X	X	X	X	X	X	X	X
Vital sign measurements ^b	X	X	_	-	-	X	-	_	-	_	-	-	-	_
Physical examination ^c	X	X	_	_	X	X	_	_	X	X	_	(X)	_	(X)
Serology screening ^d	X	_	_	_	_	_	_	_	_	_	_	_	_	_
Serology flavivirus screening by ELISA ^e	X	_	_	_	_	_	_	_	_	_	_	_	_	_
Urine drug screen ^f	X	_	_	_	-	_	_	_	_	_	_	_	_	_

Procedure	Screening Phase				Vaccina	tion Phas	e				Loi	ng-Ter	m Follow-	up Phase
Study Visit	Screening	Day 1	Day 2	Day 3	Day 8	Day 29	Day 30	Day 31	Day 36	Day 57 (Month 2)	Months 3, 4, 5, 6	Month 7	Months 8, 9, 10, 11, 12	Month 13 (EOS) ^a
Visit Number	0	1	2	3	4	5	6	7	8	9	10-	14	15-19	20
Type of Visit	C	C	SC	SC	C	C	SC	SC	C	C	SC	C	SC	C
Window Allowance	-28/0	0	0	0	+3	+14	0	0	+3	-7/+14	±7	±14	±7	±14
Urine pregnancy test ^g	X	X	_	-	_	X	_	_	_	_	_	_	-	_
Assessment of eligibility/contraindications for subsequent vaccination ^h	_	X	_	-	-	X	_	_	I	_	_		-	-
Randomization	_	X	_	_	_	_	_	_	_	_	_	_	_	_
Blood sample for clinical laboratory tests (hematology, serum chemistry, and coagulation) (Section 3.5.8)	X	X	_	_	X	X	_	_	X	X	_	_	-	-
Diary card training	_	X	_		_	X	_	_	-	_	_		-	_
Distribute diary card for collection of solicited and unsolicited AEs ⁱ	-	X	_	_	-	X	_	_	_	_	_	_	_	_
Vaccination administration	-	X	_	_	_	X	_	_	_	_	_	_	_	_
60-minute post-vaccination assessment ^j	_	X	_	_	-	X	_	_	ı	_	_	_	_	_

Procedure	Screening Phase				Vaccina	tion Phas	e				Loi	ng-Ter	m Follow-	up Phase
Study Visit	Screening	Day 1	Day 2	Day 3	Day 8	Day 29	Day 30	Day 31	Day 36	Day 57 (Month 2)	Months 3, 4, 5, 6	lor	Months 8, 9, 10, 11, 12	Month 13 (EOS) ^a
Visit Number	0	1	2	3	4	5	6	7	8	9	10-	14	15-19	20
Type of Visit	C	C	SC	SC	C	C	SC	SC	C	C	SC	C	SC	C
Window Allowance	-28/0	0	0	0	+3	+14	0	0	+3	-7/+14	±7	±14	±7	±14

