Blood sample collection for vaccine-induced immunogenicity assay ^k	-	X^{l}	_	-	ı	X ^l	_	_		X	_	X	-	X
Post-vaccination SC ^m	_	_	X	X	_	_	X	X	_	_	X	_	X	_
Return and review diary card	_	_	_	_	X	X	_	_	X	X	_	1	_	_
Record unsolicited AEs	_	X	X	X	X	X	X	X	X	X	_	-	_	_
Record SAEs, MAAEs, and AEs of special interest ⁿ	_	X	X	X	X	X	X	X	X	X	X	X	X	X

Page 90

- Abbreviations: –, not collected; AE, adverse event; C, clinic visit; AE, adverse event; AESI, adverse event of special interest; ELISA, enzyme-linked immunosorbent assay; EOS, end of study; IgG, immunoglobulin G; IgM, immunoglobulin M; MAAE, medically attended adverse event; NA, not applicable; SAE, serious adverse event; SC, safety telephone call; SOE, schedule of events.
- ^a Unless consent is withdrawn, a participant who discontinues from receiving the second dose of study vaccine will remain in the study and complete all safety and immunogenicity procedures required through 1 month after the last vaccination received per the SOE (i.e., up to Day 29 for subjects receiving only the first dose of vaccine). Subjects will then enter the 12-month Long-Term Follow-up Phase per the SOE.
- Vital sign measurements will include systolic and diastolic blood pressure, heart rate, respiratory rate, and body temperature. Oral temperature is preferred route. The participant will be seated for at least 5 minutes before all measurements are taken. Vital sign measurements will be collected once before dose administration and at least 1 hour after dose administration (before participants are discharged from the clinic) on Visits Day 1 and Day 29. When procedures overlap and are scheduled to occur at the same time point, the order of procedures should be vital sign measurements and then the blood collection.
- A full physical examination, including height and weight (and body mass index calculation), will be performed at screening (Section 3.5.10); symptom-directed (targeted) physical examinations will be performed at all other scheduled time points. Interim physical examinations will be performed at the discretion of the investigator. Investigator may perform targeted physical examinations at Month 7 and Month 13 at their discretion. A physical examination of the arm that was vaccinated and the associated lymph nodes should be evaluated before each vaccination and at 7 days post-vaccination.

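### Participants who withdraw during the Vaccination Phase are asked for the Month 13 assessments, which schedule no safety laboratory tests, no diary review and no unsolicited-AE recording

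*Protocol*

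**What the plan says.** Protocol 3.3.1 states: "Participants who are withdrawn from the study will be requested to complete the EOS (Visit 20 [Month 13]) assessments". Protocol 3.3.3 says the same: "These participants will also be requested to complete the EOS (Visit 20 [Month 13]) assessments". Neither section makes the request depend on when the participant leaves, and Table 5 has no early-termination column or footnote.

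In Table 5 the Month 13 column marks concomitant medications, an optional targeted examination, the immunogenicity sample and the recording of SAEs, MAAEs and AESIs. Three rows have no mark there:

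- the row that begins "Blood sample for clinical laboratory tests (hematology, serum chemistry, and coagulation) (Section 3.5.8", marked at Screening and Days 1, 8, 29, 36 and 57;
- "Return and review diary card", marked at Days 8, 29, 36 and 57;
- "Record unsolicited AEs", marked from Day 1 to Day 57.

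Two groups are treated differently. For someone leaving because of an AE, 3.3.1 adds that "the investigator will try to obtain agreement to follow up with the participant until the event is considered resolved or stable". Someone who stops vaccine but stays in the study keeps all safety procedures for one month after the last dose (3.3.2).

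On the analysis side, SAP 6.1.2 puts anyone who received a dose in the Safety Set. SAP 7.6 bases all safety analyses except the solicited ones on that set. SAP 7.1 makes the set's size in each group the denominator for percentages unless otherwise specified.

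**The concern.** The second primary endpoint is "Frequency and grade of any unsolicited AEs during the 28-day follow-up period after each vaccination", and the first is solicited reactions over 7 days after each dose. Both concern the Vaccination Phase, as do all post-dose laboratory draws. The exit set requested from a participant who leaves in that phase comes from the end of long-term follow-up, where these items are no longer scheduled.

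A participant who leaves on Day 5 or Day 33 can attend the exit visit in full and still provide no laboratory value for the dose just received. Under the SAP's denominator rule that participant counts as dosed with no abnormality. Protocol 3.5.8 enters every laboratory value of Grade 3 or higher as an AE, so a missing panel can also remove an event from the second primary endpoint. In a first-in-human study with 24 vaccine recipients per dose, single participants matter.

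**Working it through.** **1. The plan's own figures.** Protocol 3.6.4 gives the probability of seeing at least one AE among 24 recipients as 92% at 10% incidence and 70.8% at 5%. With 1 − (1 − p)^24, the results are 1 − 0.90^24 = 0.9202 and 1 − 0.95^24 = 0.7080. Both reproduce, and both assume that all 24 are observed.

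**2. What the exit set covers, by primary endpoint (3.6.1).**

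| Endpoint | Marked at Month 13? | Other route |
|---|---|---|
| Solicited reactions, 7 days | No | 3.5.2: unreturned cards are requested by telephone or other means |
| Unsolicited AEs, 28 days | No | 3.5.7.2: standard question at every visit or call; 3.5.7.3: all reported or observed events are recorded |
| MAAE, SAE, AESI | Yes | – |

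The diary route is the weaker one. Protocol 3.5.2 accepts the card as the sole source for solicited reactions, and a reaction told to staff at a visit is entered as unsolicited. If the card is not recovered, that reaction is lost to the first endpoint or moves to the second. A participant with no solicited data for a dose also drops out of that dose's Solicited Safety Set (SAP 6.1.3).

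**3. Laboratory tests.** No section requires them at exit. The catch-up of missed-visit items in 3.4.7 is written for participants who go on to later visits, so it does not clearly reach withdrawals.

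**4. Length of the gap.** The first post-dose draws are Day 8 (+3) and Day 36 (+3). Day 8 − Day 1 = 7 days and Day 36 − Day 29 = 7 days, or up to 10 days with the window. Someone who leaves on Day 20 after attending Day 8 has one result for the first dose. The gap with no result at all is therefore about one week after each dose.

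**5. Size, as an illustration only.** The documents give no dropout rate. Assume that k of 24 leave in that week. If leavers would have had the same risk as those who stay, a true incidence p is reported on average as p × (24 − k)/24. The chance of seeing at least one event is 1 − (1 − p)^(24 − k).

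| k | k/24 | Reported, true 10% | Reported, true 5% | P(≥1), 10% | P(≥1), 5% |
|---|---|---|---|---|---|
| 0 | 0% | 10.0% | 5.0% | 0.9202 | 0.7080 |
| 1 | 4.2% | 9.6% | 4.8% | 0.9114 | 0.6926 |
| 2 | 8.3% | 9.2% | 4.6% | 0.9015 | 0.6765 |
| 3 | 12.5% | 8.75% | 4.4% | 0.8906 | 0.6594 |

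If every leaver would have had the abnormality, the shortfall is at most k/24, the second column.

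**The case against.** The strongest reply is that the protocol already catches most of what matters. SAEs, MAAEs and AESIs are recorded at exit. An exit visit on Day 20 lies inside the unsolicited-AE collection period, and the standard question is asked there. Missing diary cards are pursued. AEs leading to withdrawal are collected throughout (3.1), and a solicited reaction that causes withdrawal must be entered as an AE (3.5.7.1.1). Section 3.5 allows unscheduled visits and further laboratory requests. All of this stands. It removes most of the concern about symptomatic events, but it does not mandate an exit laboratory panel or schedule a diary review.

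A reader might infer four stronger things that the documents do not support.

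- *That early leavers take all the primary-endpoint data with them.* The third endpoint is collected at exit, data already recorded are kept, and the other two endpoints have partial recovery routes.
- *That reaction-driven withdrawal clearly biases both AE endpoints downward.* The reaction behind a withdrawal is captured by design. What remains exposed is mainly silent laboratory abnormalities and reactions recorded only on a card that is never returned.
- *That pause rule 6 is distorted.* Its denominator is limited to participants who have provided safety data, explained as those who "have completed a post-dosing visit for assessment of safety". Even if an exit visit counted, 20% of 21, 22, 23 and 24 is 4.2, 4.4, 4.6 and 4.8, so five events are needed each time.
- *That missing vital signs belong on the list.* Visit 9 has none either, so they do not distinguish the two visit sets.

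**Conclusion.** The point holds as a modest gap in data collection. The exit set was chosen without regard to timing, and for withdrawals before Day 57 it omits scheduled laboratory tests, diary review and unsolicited-AE recording. The firm loss is the laboratory result for a participant who leaves within about a week of a dose. The diary and unsolicited-AE losses are partial.

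The likely effect is a slight understatement of laboratory abnormalities and of the Grade 3 or higher values entered as AEs. Its size cannot be set from the documents; 1 to 3 leavers of 24 is an assumption. The conclusion also assumes that the SAP's default denominator applies to the laboratory tables. A row for missing values, which SAP 7.1 allows where the shells specify it, would show the gap but not fill it. Laboratory results are not themselves a listed primary endpoint. This is a cheap improvement, not a threat to the study's conclusions.

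**What to change.** In Protocol 3.3.1 and 3.3.3, and in a footnote to Table 5, state that participants who withdraw before completing Visit 9 will be asked to complete the Visit 9 (Day 57) assessments at exit: diary return and review, unsolicited AEs, safety laboratory tests, targeted examination, immunogenicity sample, and SAE/MAAE/AESI recording. Keep the Visit 20 assessments for later withdrawals. Because Table 5 footnote k uses the end-of-study blood to test for flavivirus seroconversion, say that the exit immunogenicity sample also serves that purpose.

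The cost is two sentences and a footnote. Each early withdrawal adds 2 + 6.5 + 3 = 11.5 mL of blood (Table 4) and one central-laboratory panel. An early leaver has had at most five of the six scheduled laboratory collections, so the scheduled total in Table 4 is not exceeded. Attendance remains a request, as it is now for Visit 20, so the change reduces the gap without guaranteeing that it closes.

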3.3.2 Participant Withdrawal From Study Vaccine

Every reasonable attempt will be made to follow up with participants for safety throughout the entire study period, even if further vaccination is withheld or the participant misses one or more visits.

Unless consent is withdrawn, a participant who discontinues from receiving the second dose of study vaccine will remain in the study and complete all safety and immunogenicity procedures required through 1 month after the last vaccination received per the Schedule of Events (i.e., up to Visit 5/Day 29 for subjects receiving only the first dose of vaccine).

Subjects will then enter the 12-month Long-Term Follow-up Phase per the Schedule of Events (Table 5).

The investigator, in consultation with the Sponsor's medical monitor, **may** withhold a participant **from further vaccination** if the participant experiences any of the following:

- Becomes pregnant
- Develops, during the course of the study, symptoms or conditions listed in the exclusion criteria
- Experiences an AE (other than reactogenicity) after vaccination that is considered by the investigator to be possibly or probably related to vaccine and is of Grade 3 (severe) or greater severity (Appendix 3)
- Experiences an AE or SAE that, in the judgment of the investigator, requires study vaccine withdrawal due to its nature, severity, or required treatment, regardless of the causal relationship to vaccine
- Experiences a CS change in clinical laboratory test results, vital sign measurements, or general condition that, in the judgment of the investigator, requires vaccine withdrawal
- Experiences anaphylaxis clearly attributed to study vaccine
- Experiences generalized urticaria related to the study vaccine

The reason(s) for withdrawing further vaccination will be recorded.

3.3.3 Handling of Withdrawals

When a participant withdraws from the study, the reason(s) for withdrawal will be recorded by the investigator on the relevant page of the eCRF. These participants will also be requested to complete the EOS (Visit 20 [Month 13]) assessments.

Any participant who fails to return for final assessments will be contacted by the site with a minimum of 3 documented telephone calls, faxes, text messages, or emails and 1 registered mail letter. If participant is not reached, the participant will be defined as lost to follow-up. All attempts to contact the participant must be documented in the participant's source

documents. After the final attempt, the participant will be declared "lost to follow-up" at the EOS Visit.

3.3.4 Replacements and Rescreening

Any participant who is withdrawn, who is significantly outside the allowed vaccination window, or who is lost to follow-up from the study may be replaced at the Sponsor's discretion. Rescreening of an eligible subject is allowed if their originally intended dose level closes and their 28-day screening window is surpassed before another dose level opens. The participant will be assigned a new screening number and all screening procedures will be repeated.

3.4 Study Dosing Groups

3.4.1 Method of Assigning Participants to Dosing Groups

Participants will be randomly assigned (Day 1) in a blinded manner using the centralized Interactive Response Technology (IRT), with approximately 30 participants assigned to each cohort. Study vaccine dosing will begin with Cohort 1 (10 µg mRNA-1893 or placebo), followed sequentially by Cohort 2 (30 µg mRNA-1893 or placebo), Cohort 3 (100 µg mRNA-1893 or placebo), and Cohort 4 (250 µg mRNA-1893 or placebo). Within each cohort, participants will be randomly assigned in a blinded manner to receive either mRNA-1893 vaccine or placebo (4:1 mRNA-1893 vaccine to placebo) using the centralized IRT. Participants will be stratified according to flavivirus baseline serostatus.

In each cohort, the initial 5 participants (all seronegative) will be randomly assigned to vaccine or placebo (4:1 mRNA-1893 vaccine to placebo) before the remaining participants (n=25, 20 seronegative and 5 seropositive) are enrolled in the cohort.

Randomization by the centralized IRT will be in accordance with pre-generated randomization schedules, with only the unblinded pharmacy personnel having controlled access.

Dose group assignment in each cohort and stratification within each cohort is summarized in Table 1.

Table 1: Dose Group Assignment

	Dose Group Assignment	n	Flavivirus Status Stratification ^a		Total
Cohort			Status	n	(Ratio)
	mRNA-1893 10 μg	24	+	4	
1			-	20	30
1	Placebo	6	+	1	(4:1)
			-	5	
	mRNA-1893 30 μg	24	+	4	
2			-	20	30
2	Placebo	6	+	1	(4:1)
			-	5	
	mRNA-1893 100 μg	24	+	4	30 (4:1)
3			-	20	
3	Placebo 6	6	+	1	
		0	-	5	
	mRNA-1893 250 μg 24	24	+	4	30 (4:1)
4		24	-	20	
4	Placebo	6	+	1	
			-	5	
			-	Total	120

Abbreviations: - = flavivirus seronegative; + = flavivirus seropositive.

